4.3. Justification for dose (Amended 15 March 2022)

A single formulation of the investigational RSV maternal vaccine (containing 120 µg of the RSVPreF3 antigen) *was* planned. Available data *suggested* that the 120 µg formulation *had* an acceptable safety profile and tends to elicit stronger immune responses, which is likely to result in higher placental transfer of antibodies to the fetus than formulations containing 30 or 60 µg of the RSVPreF3 antigen. Available results from RSV MAT-001 and RSV MAT-004 studies are included in the IB to support RSV MAT-012.

Infection with RSV occurs in almost all participants by the time of reproductive age and it is extremely unlikely that a maternal participant would not have been naturally infected with RSV before. Results of study RSV MAT-001 in non-pregnant women *and RSV MAT-004 in pregnant women* indicate that a single dose of the study vaccine is sufficient to boost the neutralizing antibodies induced by previous natural infections.

The study vaccine will be administered* between 24^{0/7} and 36^{0/7} weeks of gestation (inclusive). This gestational age range is considered optimal for both immunogenicity and safety. It allows enough time to (a) induce high neutralizing antibody levels in maternal participants before term delivery and (b) ensure these antibody levels are elevated during the period of greatest placental antibody transfer to the fetus. Moreover, it is after the critical period for organogenesis (i.e. after the period when most congenital abnormalities develop).

**** Due to the recent safety signal, there will be no further enrollment and vaccination of maternal participants. For details, refer to [Section 2.3](#).***

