Child:	A young human being below the legal age of majority (generally < 18 years of age).
Eligible:	Qualified for enrollment into the study based upon strict adherence to inclusion/exclusion criteria.
End of Study (EoS) (Synonym of End of Trial)	EoS occurs with the last infant participant last visit (LSLV; Visit 5-NB).
Enrolled participant	
‘Enrolled’ means a maternal participant’s/infant parent’s/LAR’s agreement to participate in a clinical study following completion of the informed consent process. Potential maternal participants who are screened for determining eligibility for the study, but do not participate in the study, are not considered enrolled, unless otherwise specified by the protocol.
 
Refer to the Section 9.3 of the protocol for the definition of ‘enrolled set’ applicable to the study.

Essential documents	Documents which individually and collectively permit evaluation of the conduct of a study and the quality of the data produced.
eTrack:	GSK’s tracking tool for clinical trials.
Evaluable:	Meeting all eligibility criteria, complying with the procedures defined in the protocol, and, therefore, included in the per protocol analysis (see Section 9.3 for details on criteria for evaluability).
GAIA	Global Alignment of Immunization Safety Assessment in pregnancy. A project that aims to improve the quality of outcome data from clinical vaccine trials in pregnant women with a specific focus on the needs and requirements for safety monitoring in low to middle income countries.

Gestational age:	A measure of the age of a pregnancy where the origin is the first day of the woman's last normal menstrual period, or the corresponding age as estimated by other methods. Gestational age will be described in weeks of pregnancy completed + number of days completed of the following week. For example: 28 ^{0/7} means completed 28 weeks of pregnancy + 0 days of the 29th week and 28 ^{6/7} means completed 28 weeks of pregnancy + 6 days of the 29th week.
Immunological correlate of protection:	A correlate of risk that has been validated to predict a certain level of protection from the targeted endpoint.
Infant	A child younger than 1 year of age
Intervention	Term used throughout the clinical study to denote a set of investigational product(s) or marketed product(s) or placebo intended to be administered to a participant.
Intervention number:	A number identifying an intervention to a participant, according to intervention allocation.

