4.3.3. Sensitivity analyses

For primary and secondary immunogenicity endpoints, between study group comparisons will also be explored through statistical modelling. This analysis is exploratory.

For the analysis of maternal participants at each time point (Day 31, Delivery), the ANCOVA model will be explored and fitted via the proc GML procedure according to the following code:

```
PROC GLM data=adis_moth;
  BY atptn atpt;
  CLASS tr01aga gagevg1 agegr3;
  MODEL aval = base tr01aga gagevg1 agegr3 vacdel;
  LSMEANS tr01aga/pdiff cl alpha=0.05;
RUN;
```

where aval represents the log-transformed antibody value of the immunogenicity variable at a given post baseline timepoint, group indicates the study group, gagevg1 is the gestational age category at study intervention administration ($<28^{0/7}$, $\geq 28^{0/7}$ weeks), agegr3 is the age category at study intervention administration (<18 years and ≥ 18 years), vacdel is the interval between vaccination and delivery (days). The inclusion of age category at study intervention administration, interaction term between age category and gestational age category and interval between study intervention administration and delivery in the model depends on the availability of the variables (vacdel may not be available at Day 31 analysis) and the necessity, therefore, the above SAS code serves as a reference and may be adjusted according to the analysis needs. Other possible co-variables which could be included in the model, but not limited to, are pre-existing HIV infection status, CD4 count, COVID-related complications.

For the analysis of infants at each time point (cord blood at Delivery, Day 43 post-birth, Day 121 post-birth, and Day 181 post-birth), similar model will be explored:

```
PROC GLM data=adis;
  BY atptn atpt;
  CLASS tr01aga gagevg1 gagebg1 agegr3;
  MODEL aval = base tr01aga gagevg1 gagebg1 agegr3;
  LSMEANS tr01aga/pdiff cl alpha=0.05;
RUN;
```

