Baseline is pre-vaccination logarithm10 transformation of the concentrations/titers from maternal participants, gagebg1 is gestational age category at birth (> 37 weeks; ≤ 37 weeks) for infant participants. With the inclusion of gestational age category at vaccination (gagevg1) in the model, this categorical variable gagebg1 provides similar information as continuous variable vacdel, therefore the inclusion of either variable in the model could be adjusted according to the analysis needs. Other possible co-variables which could be included in the model, but not limited to, are maternal pre-existing HIV infection status, CD4 count, COVID-related complications, infant HIV infection status.

The ratio of GMTs/GMCs between study intervention groups and the corresponding 95% CI will then be constructed by exponentiating the mean difference and its confidence interval between study intervention groups on the logarithm10 scale estimated from the model. Summary tables will show adjusted GMT/GMC for study intervention groups, and ratios of GMTs/GMCs between study intervention groups along with the 95% CI.

Summary tables will present number of observations included in the model, the model adjusted GMT/GMC for each group and between group adjusted GMT/GMC ratio with the corresponding 95% CIs at each timepoint.

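### The antibody ANCOVAs carry gestational age at dosing only as <28/≥28 weeks, at a small cost in precision, chiefly in the infant model and at maternal Day 31

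*SAP*

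**What the plan says.** Protocol 5.1.1 admits women dosed from 24 0/7 to 36 0/7 weeks, and Protocol 10.7.2 fixes the resolution: "Gestational age will be described in weeks of pregnancy completed + number of days completed of the following week". Protocol 6.3.3 minimises on gestational age at dosing in two classes, below 28 weeks and 28 weeks or later.

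The ANCOVA text in SAP 4.2.2.1 and 4.3.2.1 uses the same two classes. For mothers and infants alike it also lists the interval between dosing and delivery, to be included if needed.

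SAP 4.3.3 gives reference code:

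- Maternal: "MODEL aval = base tr01aga gagevg1 agegr3 vacdel". Here "gagevg1 is the gestational age category at study intervention administration", and vacdel is the dosing-to-delivery interval in days. The SAP warns that "vacdel may not be available at Day 31 analysis".
- Infant: "MODEL aval = base tr01aga gagevg1 gagebg1 agegr3". The term gagebg1 is gestational age at birth, above 37 weeks or not. There is no vacdel. The stated reason is that, with gagevg1 in the model, "this categorical variable gagebg1 provides similar information as continuous variable vacdel", so that either may be used.

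SAP 4.3.3 labels this modelling exploratory and the code adjustable. SAP 2 states that no hypothesis is tested.

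**The concern.** The upper class spans eight weeks, so without a continuous timing term women dosed at 28 0/7 and at 36 0/7 have the same covariate value. Protocol 4.3 gives reasons to expect timing to matter: the dosing window should leave time for a response before term delivery and "ensure these antibody levels are elevated during the period of greatest placental antibody transfer to the fetus". If week of dosing within a class predicts antibody level, that variation stays in the error term. Minimisation on the same two classes does not balance it either.

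The infant model is the clearest case, because its code omits the continuous interval that the SAP's own infant ANCOVA text lists. At stake is the width of the interval around the adjusted GMT/GMC ratio, and a chance difference in mean week of dosing between arms that a collected pre-dosing value could correct.

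**Working it through.** **The plan's own precision figure.** SAP 5.2 gives half-widths of 0.056 and 0.074 on the log10 scale for a fold increase with N = 226 and SD 0.3 and 0.4. The formula t(0.975, 225) × SD × √(2/226) gives 0.0556 and 0.0742, so these reproduce. No precision is stated for the ANCOVA group contrast.

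**Assumptions that are not in the documents.** Gestational age at dosing is uniform on 24 to 36 weeks, or triangular and late-skewed (peak at 32). Gestational age at birth has mean 38 weeks and SD 1 to 2.5. The slope of log10 antibody on gestational age, b, is 0.01 to 0.05 per week. Residual SD is 0.4, the larger value in SAP 5.2.

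**What the two classes leave over.** Under uniform dosing the total variance is 12²/12 = 12. Within classes it is (1/3)(4²/12) + (2/3)(8²/12) = 0.44 + 3.56 = 4.0, an SD of 2.0 weeks, so 33% remains. Simulation of 400,000 pregnancies gives the other entries.

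| Timing terms in the model | Gestational-age variance left, uniform | Late-skewed |
|---|---|---|
| gagevg1 only (maternal Day 31 without vacdel) | 33% | 48% |
| gagevg1 + gagebg1 (infant code) | 33% | 48% |
| gagevg1 + vacdel (maternal delivery code) | 7–19% | 12–31% |
| Continuous gestational age added | 0% (linear part) | 0% |

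The gagebg1 term recovers none of the gestational age at dosing that gagevg1 loses.

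**The equivalence statement.** Take infants whose mothers were dosed at 28 weeks or later and who were born after 37 weeks. The interval can be 8 days (36 0/7 to 37 1/7), or 28 days where the infant per-protocol rule applies. It can also be 91 days (28 to 41 weeks, taking 41 as a late birth). All share one cell. In simulation the two categories explain roughly half to two-thirds of the variance of vacdel, leaving a residual SD of about two weeks.

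**Chance imbalance between arms.** With 226 vaccine and 113 placebo participants (2:1) and a within-class SD of 2.0, SE = 2.0 × √(1/226 + 1/113) = 0.23 week, and 1.96 × 0.23 = 0.45 week. At half that size (113 vs 57) the limit is ±0.64, and at one third (75 vs 38) ±0.78.

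**Effect on the ratio.** The shift is 10^(b × 0.45), a factor of 1.01 at b = 0.01 and 1.05 at b = 0.05. At one third of planned size it is 1.02 to 1.09. For comparison, the 95% half-width of the group contrast at 226 vs 113 is 1.96 × 0.4 × √(1/226 + 1/113) = 0.090, a factor of 1.23.

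**Effect on precision, by slope.** √(0.4² + b² × 2.0²)/0.4 gives 1.001, 1.005 and 1.031 for b = 0.01, 0.02 and 0.05, so the SE is 0.1%, 0.5% or 3% larger.

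**Effect on precision, by variance explained.** Let gestational age explain a share R² of residual variance and the two classes keep a share r² of it. Then the width ratio, classes over continuous, is √((1 − R² r²)/(1 − R²)). The value of r² is 0.667 for uniform dosing, and 0.529 or 0.486 for triangular dosing with a peak at 30 or 34 weeks.

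- R² = 5%: about 1% wider.
- R² = 10%: 2 to 3% wider.
- R² = 20%: √(0.867/0.8) = 1.04 for uniform dosing and √(0.903/0.8) = 1.06 for the peak at 34, so 4 to 6% wider.

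For the maternal delivery model with vacdel, R² = 20% gives only about 1 to 2% (uniform) or 1.5 to 4% (late-skewed).

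**The case against.** A reader might infer that up to eight weeks of gestational-age difference remains in the vaccine–placebo contrast. The documents do not support that. Eight weeks is the spread between individuals in one class. Allocation is randomised and minimised on that class, so the expected difference between arms is zero and only chance imbalance remains.

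A reader might also infer that every model treats women dosed at 28 and 36 weeks as identical. That is wrong for maternal delivery: two such women delivering at the same gestational age differ by 56 days in vacdel. The ANCOVA text also lists the interval for infants, and SAP 4.3.3 allows it in the infant model in place of gagebg1.

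Other points stand in part. Protocol 4.3 calls the whole 24 to 36 week window optimal and gives no slope within it, so the prognostic strength is assumed. The analysis is exploratory, adjustable and tests nothing, and using a minimisation factor in the form used for allocation is conventional. A single linear slope common to both arms is itself an assumption: timing of placebo need not act as timing of vaccine does, and the gains shown depend on it.

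None of this rescues the equivalence statement, or explains why the infant code omits a term that the infant ANCOVA text lists. These models also supply the adjusted ratios and intervals for the summary tables.

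**Conclusion.** The point holds as a minor matter of precision. Gestational age at dosing is dichotomised in every antibody ANCOVA although it is available to the day. The effect is greatest in the infant reference model, and in the maternal Day 31 model if vacdel is missing. In the maternal delivery model vacdel recovers most of the information, leaving 7 to 31% of gestational-age variance.

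There is no systematic bias. The loss is about 0 to 3% in SE for the assumed slopes, and 4 to 6% in interval width if gestational age explained 20% of residual variance. Uncorrected chance imbalance is about ±0.45 week at planned size. Enrolment stopped early and the achieved number is not given, so the imbalance could be larger. The slopes, variance shares and distributions of dosing and birth are all assumptions.

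One related inconsistency affects the size. SAP 3.2.3.1, Table 7, code 2010 gives the gestational-age window as 28 0/7 to 36 0/7, against 24 0/7 to 36 0/7 in Protocol 5.1.1. Applied literally, it would leave gagevg1 with one level in the per-protocol set, where it would adjust for nothing. The passages must be reconciled.

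**What to change.** - In both PROC GLM models, and in the matching ANCOVA wording of SAP 4.2.2.1 and 4.3.2.1, add gestational age at dosing as a continuous covariate in weeks (days/7). Keep gagevg1 as the minimisation factor.
- In SAP 4.3.3, delete only the statement that gagebg1 gives similar information to vacdel. Keep the permission to use either variable, since that is what allows a continuous interval in the infant code.
- Reconcile the infant code with the infant ANCOVA text, stating which timing terms will be fitted.
- Fit at most two of continuous gestational age at dosing, vacdel and continuous gestational age at birth. The first two sum to the third once units match, so all three cannot be estimated together.

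The cost is one added term per model, one degree of freedom and a few words in the SAP. No new data are needed.

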4.2.2. Immunogenicity

4.2.2.1. Analysis of immunogenicity planned in the protocol

The primary analysis for immunogenicity will be based on the PPS for analysis of immunogenicity.

	Primary Immunogenicity Endpoints	Statistical Analysis Methods
Maternal participants	
 • Humoral immune responses at pre-dosing (Day 1) and at delivery: 
 – RSVPreF3 IgG-specific antibody concentrations – Neutralizing antibody titers against RSV-A 	
For each assay, at each timepoint and by study group and age category (<18 years; ≥ 18 years; overall):
 
 • Antibody titers/concentrations will be displayed using reverse cumulative curves. • GMTs/ GMCs will be tabulated with 95% CI and represented graphically. • GMR of antibody titers/concentrations at delivery over pre-dosing will be tabulated with 95% CI. 
Between group evaluation in terms of RSVPreF3 IgG-specific antibody concentrations and neutralizing antibody titers against RSV-A will be performed at delivery using an ANCOVA model on the logarithm₁₀ transformation of the concentrations/titers, and including the pre-dosing logarithm₁₀ transformation of the concentrations/titers, the study intervention, gestational age at the time of study intervention administration (<28^{0/7}; ≥ 28^{0/7} weeks), and the interval between dosing and delivery as covariates if needed.

Cord blood/placental transfer	
Ratio between cord blood* and maternal RSVPreF3 IgG-specific antibody concentrations at delivery.
 
*or infant blood sample collected within 72 hours after birth (if no cord blood sample can be obtained).
	
 • Geometric mean of placental transfer ratio will be tabulated with 95% CI by study group. • Percentage of infants with placental transfer ratio ≥ 1 will be tabulated with exact 95 % CI by study group.

	Primary Immunogenicity Endpoints	Statistical Analysis Methods

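### The between-group antibody ratio may be adjusted for delivery timing, which is fixed after randomisation, so it need not equal the randomised effect of the vaccine

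*SAP*

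**What the plan says.** SAP 4.2.2.1 specifies, for the primary immunogenicity endpoints in mothers and infants, a between-group ANCOVA on log10 titre or concentration. Its terms are the pre-dose value, arm, gestational age at dosing (cut at 28 weeks) "and the interval between dosing and delivery as covariates if needed". SAP 4.3.2.1 repeats the clause for the secondary endpoints, including maternal Day 31, and Protocol 9.4.3.2 and 9.4.4.2 carry it too.

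SAP 4.3.3 gives the code. The maternal model is "MODEL aval = base tr01aga gagevg1 agegr3 vacdel", and "vacdel is the interval between vaccination and delivery (days". The infant model is "MODEL aval = base tr01aga gagevg1 gagebg1 agegr3", and "gagebg1 is gestational age category at birth (> 37 weeks; ≤ 37 weeks) for infant participants". The SAP treats the two delivery-related variables as carrying similar information, so that "the inclusion of either variable in the model could be adjusted according to the analysis needs".

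The same section calls the modelling exploratory and the code a reference that may be changed. It also makes the model-adjusted GMT/GMC and the between-group ratio with 95% CI the content of the summary tables.

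**The concern.** Randomisation and dosing take place at Visit 1, and the interval to delivery and gestational age at birth are settled only at delivery. Adjusting for them is harmless to the randomised comparison only if the vaccine does not affect when women deliver. The sponsor cannot assume that here. Protocol 2.3 says enrolment and vaccination stopped on 25 February 2022 after a preterm-birth imbalance between arms in RSV MAT-009, cause undetermined. Preterm birth is itself a primary infant endpoint of this trial (SAP Table 1), and gagebg1, split at 37 weeks, is close to that endpoint. An antibody ratio adjusted for it answers a question about vaccinating at a given delivery time, and the SAP states no estimand for that.

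Two features add to this. At Day 31 the interval is generally completed after the blood sample was taken, because women who deliver before Day 31 have no Visit 2. And the choice of covariate is left open in an amended SAP dated 1 June 2022, when the trial had already been fully unblinded.

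**Working it through.** **1. The plan's own precision figure.** SAP 5.2 gives SD 0.4 (log10), n = 226 and half-width 0.074. Treating pre- and post-dose values as uncorrelated: 1.96 × 0.4 × √2 / √226 = 0.0738. A 9-fold rise then has 95% CI 7.6 to 10.7, as stated. The SAP gives no such figure for the between-group ratio.

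**2. A yardstick for the between-group ratio.** With 226 vaccinees and 126 × 0.9 ≈ 113 controls: 1.96 × 0.4 × √(1/226 + 1/113) = 0.090 log10, a factor of 10^0.090 = 1.23 either way. This uses planned numbers. Actual enrolment after the stop is not given, and fewer women would widen it; adjusting for baseline would narrow it.

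**3. What adjustment does.** Let b be the common slope of log10 titre on the interval in the ANCOVA, and let the vaccine shorten the mean interval by d days. With other covariates balanced by randomisation:

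adjusted log10 ratio − total log10 ratio = b × d

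The departure is zero if d = 0, and its sign follows the sign of b.

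**4. Assumed inputs (none is in the documents).** Direct vaccine ratio 10-fold; independent SD of the interval 25 days; slope in vaccinees −0.004 to +0.004 log10 per day; slope in placebo 0; d = 0, 2, 5 or 10 days; with or without an unmeasured common cause that moves the interval by 8 days and titre by 0.1 log10 per SD.

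With 2:1 allocation the pooled slope is 2/3 × (±0.004) = ±0.00267. The common cause adds (8 × 0.1)/(25² + 8²) = 0.8/689 = 0.00116, so the largest positive slope is 0.00383.

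**5. Adjusted ratio divided by total randomised ratio, 10^(b × d).**

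| d (days) | b = −0.00267 | b = +0.00267 | b = +0.00383 | Simulated range |
|---|---|---|---|---|
| 0 | 1.000 | 1.000 | 1.000 | 0.997–1.003 |
| 2 | 0.988 | 1.012 | 1.018 | 0.988–1.020 |
| 5 | 0.970 | 1.031 | 1.045 | 0.968–1.047 |
| 10 | 0.940 | 1.063 | 1.092 | 0.936–1.095 |

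The last column is from a simulation of 226 against 113 women, 1,500 runs per scenario, covering all the slopes with and without the common cause. In the same runs the model without the interval recovered the total effect within 0.5%.

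If the placebo slope is set equal to +0.004 instead of 0, the 10-day factor is 10^0.04 = 1.10, or 10^0.0516 = 1.13 with the common cause. That is still inside 1.23.

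**The case against.** Much of the case for leaving the plan alone is fair. No written model contains both variables; each enters conditionally, and the code is only a reference. The analysis is descriptive, with no hypothesis tested. Unadjusted GMTs/GMCs with CIs are tabulated by group, SAP 4.1.1 gives a CI method for a group ratio, and SAP 6.1.2.1 summarises the interval by group, so a shift would be visible. The evidence for a shift comes from another trial, in healthy women, with no cause established. A model conditional on delivery timing is also a legitimate description of antibody transfer. All of this stands and limits the seriousness of the point.

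It does not remove it. The ANCOVA is the only between-group comparison listed under the primary immunogenicity endpoints (the geometric mean ratio there is delivery over pre-dose), and its adjusted ratio is what the tables show. The SAP's remark that vacdel may be unavailable for Day 31 gives little protection, because the one remaining main analysis is at study end, when delivery dates will normally be known.

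A reader might infer that the adjustment flatters the vaccine by hiding antibody lost through early delivery, on the view that the interval matters only for vaccine-induced antibody. The documents do not support this. They give no slope, so the direction is open. Protocol 4.3 says almost all women have had RSV before and refers to a period of peak placental transfer, so delivery timing may matter for cord titres in the placebo arm as well.

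**Conclusion.** The point holds conditionally. The plan allows the reported between-group ratio to be adjusted for a variable fixed after randomisation that the vaccine may influence, so the ratio need not equal the randomised effect. Under the assumed inputs the departure is about 2%, 5% and 10% for shifts of 2, 5 and 10 days, in either direction. That is small against a roughly 10-fold ratio and inside the planned interval, but a systematic departure does not shrink with sample size.

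Two stronger readings go too far. One is that the adjusted ratio is wrong as it stands; that requires the vaccine to move delivery in this trial, which is not known. The other is that removing these covariates would restore a fully randomised comparison. The infant per-protocol set (SAP Table 4) excludes births less than 4 weeks after dosing, itself a post-randomisation event.

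**What to change.** In SAP 4.2.2.1, 4.3.2.1 and 4.3.3, take the reported between-group GMT/GMC ratio from one model fixed in advance: log10 pre-dose value (maternal, for infants), arm, gestational age at dosing in days, age stratum and HIV/obstetric status. Protocol 6.3.3 defines that status only for women of 18 or over, so age and status are best coded as one four-level factor. Leave the delivery interval out of the Day 31 model. Keep any vacdel or gagebg1 model as a supplementary analysis labelled as conditional on delivery timing. State that the infant comparison still depends on the 4-week exclusion. Record the change in SAP 4.8, since the protocol names the same covariate.

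The cost is SAP text, edits to two models and possibly a slightly wider CI. Using gestational age at dosing in days should recover much of the lost precision. If dosing is spread evenly over weeks 24 to 36 (assumed), its SD is 84/√12 ≈ 24 days. With an assumed SD of 10 to 20 days for gestational age at birth, independent of dosing, it carries 588/(588 + 100) to 588/(588 + 400), about 85% to 60%, of the variance of the interval.
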